4. STUDY DESIGN

4.1 Type of Study

The study will be a single-blind, multi-center, phase IV randomized controlled trial enrolling healthy neonates that are ≤ 1 week of age. The main recruitment center will be the Maternity Ward of Hospital Nacional Simão Mendes (HNSM), which has approximately 8,000 births/year. The HNSM Director approved to host the trial on September 12, 2025. The trial will begin at HNSM (**Phase I**), and then expand to additional recruitment units, pending approval from each health facility:

Phase II:

Bandim Health Center (~200 births per year).

Hospital de Cumura (~700 births per year).

Hospital Militar (~1,000 births per year).

All inclusion sites are located in the greater Bissau area of Guinea-Bissau. We aim to recruit at least 14,500 children (see sample size calculation) during a 2-year period. Eligible newborns will be randomized 1:1 to receive a neonatal dose of monovalent HBV0 co-administered with BCG + OPV0 vs only BCG + OPV0.

Trial design and participant recruitment: Eligibility screening will occur at discharge from the birth facility, or at the health facility when a newborn born elsewhere comes for vaccination. If the mother is a known Hepatitis B carrier, the child will be excluded and offered Hepatitis B vaccine. Newborns are eligible if they are clinically stable and unvaccinated. Moribund neonates and children with major malformations will be excluded. Informed written consent will be obtained from mothers/guardians following an oral explanation in Portuguese Creole and a written trial explanation in Portuguese. Participation is voluntary, and families may withdraw from the trial at any time. Baseline information such as maternal and neonate mid-upper-arm circumference, maternal BCG scar status, socio-economic factors and phone contacts for the mother, the father and family members will be collected, as done previously.[3,5,6]

Randomization and blinding: Randomization will be performed using sealed envelopes prepared in blocks of 24, stratified by sex and place of inclusion. After the informed consent procedure, the mother/guardian selects a sealed envelope allocating the neonate to either the intervention group (HBV0) or the control group. The mother/guardian and the inclusion team will not be blinded to group allocation. All outcome assessors involved in follow-up procedures and the trial statistician will be blinded, ensuring objective outcome assessment while maintaining operational feasibility.

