4.4 Number of Subjects (Sample Size)

Based on a recently completed trial of BCG-Denmark+OPV0 vs BCG-Bulgaria+OPV0[6], conducted with the proposed setup and follow-up methodology, we anticipate a 6-week mortality rate of 1.4% and a non-fatal infectious disease admission rate of 2.6%, for a composite risk of 4% in the control group. The number of dropouts in previous trials has been low, and the composite risk of 4% is based on the collected data in the most recent trial[6], e.g., the rate accounts for loss to follow-up. If the rate of the composite outcome of all-cause mortality and non-fatal hospital admission with infection is 4% (0.04) in the control group, and HBV0 increases the rate of the composite outcome by 25% (to $1.25 \times 0.04 = 0.05$) or decreases the rate by 22% (to $0.78 \times 0.04 = 0.0312$), to have 80% power to detect such changes for the primary outcome, with alpha error <0.05, the required sample size is 14,368 newborns, 7,184 in each group, from sampsi .050 .040, a(0.05) p(0.80) and sampsi .040 .0312, a(0.05) p(0.80) in Stata/BE version 18.0. For simplicity, enrolling 14,500 newborns is expected to be possible before HBV0 is introduced in Guinea-Bissau. With a composite outcome prevalence of 4% (0.04), the number of deaths and non-fatal infectious disease admission expected is $7,250 \times 0.04 = 290$. With 290 events in the control group, expected to be reached when 7,250 newborns have been recruited in each trial arm, the trial has 80% power to detect if HBV0 has a beneficial non-specific effect, decreasing the rate of the primary outcome by $\geq 22\%$ or a detrimental non-specific effect, increasing the rate by $\geq 24\%$. This design ensures statistical power and precision to detect also minor NSEs of HBV0, with no known disadvantages to participants. The exact timepoint that the trial will end is determined by the time when the Ministry of Health introduces HBV0 in Guinea-Bissau. We will therefore continue the trial until HBV0 is introduced in Guinea-Bissau or when 25,000 neonates have been enrolled in the trial, whichever comes first. If 25,000 neonates are enrolled in the trial, we will be able to detect an increase in the rate of the composite outcome of 18% and a decrease of 17%.

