8.2 Statistical Analysis

The Statistical Analysis Plan (SAP) will be drafted by the trial group and submitted to the DSMB for approval. Upon approval and before initiation of data analysis, the SAP will be uploaded to an online repository. When requested by the DSMB, the trial data can be unblinded, analyzed and reported according to the SAP.

The primary endpoint for the trial will be the composite outcome of all-cause mortality and first non-fatal infectious disease admission up to 42 days of age with censoring at the time of an event, loss to follow-up, or by 42 days of age, whichever comes first. Cumulative curves for mortality and hospitalization risk will be computed using the mean cumulative function, overall, and by sex. Person-years of risk will be calculated from enrollment (day, hour and minute of randomization).

The risk of the single-event composite outcome (all-cause mortality or first non-fatal admission with infection) will be estimated using Cox proportional hazards models with age as the underlying time scale, thus inherently adjusted for age. The Cox models will provide hazard ratios (HRs) from single-event analyses of the composite outcome (all-cause mortality or first non-fatal admission with infection) up to 42 days of age (primary endpoint). Incidence rate ratios for secondary endpoints relating to long-term follow-up for mortality and admissions will be estimated using recurrent-event Andersen-Gill Cox proportional hazards models with robust standard errors. Infants will not be considered at risk of admission while admitted. Randomization will be stratified by sex and place of enrollment in blocks of 24; we will therefore include different underlying baseline hazard functions by sex and place of enrollment in the Cox models. The Cox regression models will have age as the underlying time scale and account for the survival interdependency among twin pairs by using the Stata cluster command.

Tests for proportionality of hazard rates will be computed using Schoenfeld residuals, and by visual inspection of cumulative risk curves drawn using the Kaplan-Meier method.

In-hospital case-fatality risk will be estimated using binomial regression providing risk ratios (RRs), also using the Stata cluster command. In case there are fewer than five events in one group, Fisher's exact test will be used to compute a p-value.

Cognitive scores will be standardized and tested using linear regression models.

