8.3 Subgroup Analyses

For mortality and morbidity outcomes, there will be assessment of outcomes by other ages and of outcomes assessed in more specific ways, as also outlined above.

- The composite outcome of all-cause mortality and non-fatal admission with infection by 42 days of age and by 2 years of age
- All-cause mortality by 42 days of age and 2 years of age.
- In-hospital case-fatality for all-cause and infectious disease admissions by 42 days of age and 2 years of age.
- Morbidity: hospital admissions and in-hospital case-fatality rate for major diseases groups (sepsis, respiratory infections, bronchitis, diarrheal diseases, malaria, malnutrition-related diseases) by 42 days of age and by 2 years of age.

Potential effect modification

Based on literature-identified potential effect modifiers, we will assess whether the effect of HBV0 is modified by the following potential effect modifiers (in addition to sex): vaccination campaigns, the BCG scar status of the mother at enrollment, inclusion weight ($\geq 2,500\text{g}$, between $\geq 2,000\text{g}$ to $<2,500\text{g}$, and $<2,000\text{g}$), season, mode of delivery (vaginal or Caesarean section) and whether the baby was born at a hospital or elsewhere. We will conduct a supplementary analysis to assess

HBV0's effects by age at enrolment (within 24 hours and ≥ 24 hours after birth), our hypothesis being that HBV0 will have the most marked effects among the youngest neonates. For the composite outcome by 42 days of age and by 2 years of age, we will calculate the female/male ratio.

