13 APPENDIX

13.1 Trial Inclusion Form.

Regno (birth number, HNSM): _____ Adhesive study number: _____ Written study number: _____

Date ____/____/20____ Inclusion assistant: _____ Place of enrollment: _____

The child already received a vaccine: Yes____ No____ Is sick or has a malformation: Yes____ No____

Age ≤1 week: Yes____ No____ Can be included: Yes____ No____

Information about the parents

Relation to the child ____ (1: Mother, 2: Father, 3: Uncle/aunt, 4: grandparent, 5: Other)

The mother is alive: Yes____ No____ If no, date of death: ____/____/202____

Mother's name _____

Telephone number, Orange: _____ Telephone number, Airtel: _____

Does not have a telephone____ Does not remember telephone number____ House name _____

Age____ Ethnicity_____ Schooling_____ From BHP area Yes____ No____ BHP address

information: Neighborhood and zone (TaBz)_____ House number (CaMo)_____ Child ID

(CNO)_____ Neighborhood (if not BHP area)_____

Mother's place of birth_____

Father's name _____

Telephone number, Orange: _____ Telephone number, Airtel: _____

Does not have a telephone____ Age____ Ethnicity_____ Went to school

Yes____ No____ Unknown____ Father lives with mother Y____ N____

Other contacts and relation to the child

Name contact 1 _____ Relation _____ N° _____

Name contact 2 _____ Relation _____ N° _____

Name contact 3 _____ Relation _____ N° _____

Measurements

Mother: Arm circumference____ mm Has BCG scar Yes____ No____ Width____ Height____ Assistant____

Father: Arm circumference____ mm Has BCG scar Yes____ No____ Width____ Height____ Assistant____

Information about the child

Name (if named) _____ Birth date ____ / ____ /202 ____

Time of birth ____ : ____ birthplace _____ C-section Yes ____ No ____

Sex Male ____ Female ____ Twin Yes ____ No ____ Twin number _____ Twin study number _____

Height ____ Head circumference ____ Admitted before enrolment Yes ____ No ____ Where _____

If admitted, date of hospital admission ____ / ____ /20 ____ Date of discharge ____ / ____ /20 ____

Birth weight _____ Weight on day of inclusion _____

Confirmed the child's sex (assistant name): _____

The mother or guardian of the child provided consent for participation in the trial: Yes ____ No ____

Observations _____

Randomization

Date of randomization ____ / ____ /202 ____ Time of randomization ____ : ____

Randomization lot number _____

Randomization result: HBV0 _____

Randomization result: No HBV0 _____

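### The primary Cox model uses no prognostic covariate; prespecifying inclusion weight would bring a small power gain and remove chance weight imbalance, at little cost

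*Protocol*

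**What the plan says.** Protocol 8.2 specifies the primary model in some detail: single-event Cox regression to 42 days, age as time scale, robust clustering for twin pairs, and a commitment to "include different underlying baseline hazard functions by sex and place of enrollment in the Cox models". Sex and place are the two randomization strata (Sections 4.1 and 6.3). No other baseline variable enters.

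Weight appears in two other places. The inclusion form (13.1) has fields for birth weight and for "Weight on day of inclusion", set out ahead of the randomization block. Section 8.3 will assess "whether the effect of HBV0 is modified by the following potential effect modifiers (in addition to sex"), and its list includes inclusion weight in three groups: at least 2,500 g, 2,000 to under 2,500 g, and under 2,000 g.

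Section 8.2 also says that a statistical analysis plan will be approved by the DSMB and posted before analysis starts.

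**The concern.** Nothing in the design balances weight. It is not a randomization stratum, and 6.2.2 sets no lower weight limit; 8.3 expects newborns under 2,000 g. The background (2.1) discusses neonatal death specifically in low-birth-weight babies, so weight is a natural candidate predictor of an outcome that includes all deaths to 42 days.

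If weight is prognostic, a model without it gives a hazard ratio pulled slightly towards 1 and leaves any chance difference in weight between the arms in the primary estimate. Should the arms differ visibly on weight, readers will ask for the weight-adjusted result. If that analysis is chosen after unblinding, two hazard ratios then compete. Naming one model beforehand settles the matter.

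**Working it through.** **1. Inputs from Protocol 4.4 and 4.1.** Control risk 4%: "we anticipate a 6-week mortality rate of 1.4% and a non-fatal infectious disease admission rate of 2.6" per cent. Power: "to have 80% power to detect such changes for the primary outcome". Allocation: "Eligible newborns will be randomized 1:1 to receive a neonatal dose of monovalent HBV0". Effects: "sampsi .050 .040, a(0.05) p(0.80) and sampsi .040 .0312, a(0.05) p(0.80". At 7,250 per arm, 290 control events are expected.

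**2. The plan's own figure.** It states "with alpha error <0.05, the required sample size is 14,368 newborns, 7,184 in each group". For 0.04 against 0.0312, two-sided 0.05:
- Uncorrected: n₀ = [1.960·√(2·0.0356·0.9644) + 0.842·√(0.04·0.96 + 0.0312·0.9688)]² / 0.0088² = 6,959 after rounding up.
- With continuity correction: n = (n₀/4)·[1 + √(1 + 4/(n₀·0.0088))]² = 7,184 per arm, or 14,368 in total. This is an exact match.

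**3. Unadjusted power at HR 1.25.** Events = 290 + 290 × 1.25 = 652.5. z = √(652.5/4) × ln 1.25 = 12.77 × 0.2231 = 2.850. Power = Φ(2.850 − 1.960) = 81.3%.

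**4. Assumptions on weight.** The protocol gives neither the weight distribution nor its effect. Assumed shares, heaviest group first: 87%, 9%, 4%. Assumed relative risks: four patterns from 1/1.5/3 to 1/3/10.

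**5. Formulas.**
- CV² = (variance of risk across weight groups) / (mean risk)².
- Gain in z² ≈ R² = CV² × p/(1 − p), with p = (0.04 + 0.05)/2 = 0.045, so p/(1 − p) = 0.0471.
- Adjusted z = 2.850/√(1 − R²).
- 95% limit of the HR shift from chance imbalance = exp(1.96 × √(2·CV²/7,250)).

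Worked for 1/2/4: mean = 0.87 + 0.18 + 0.16 = 1.21; mean square = 0.87 + 0.36 + 0.64 = 1.87; CV² = 1.87/1.4641 − 1 = 0.277. R² = 0.277 × 0.0471 = 0.013. Shift = exp(1.96 × √(0.554/7,250)) = 1.017. Adjusted z = 2.869, power 81.8%.

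| Pattern | CV² | R² | Power gain, formula | Power gain, simulated | HR shift, 95% limit |
|---|---|---|---|---|---|
| 1/1.5/3 | 0.132 | 0.6% | 0.2 | 0.1 to 0.3 | 1.2% |
| 1/2/4 | 0.277 | 1.3% | 0.5 | 0.5 to 0.6 | 1.7% |
| 1/3/8 | 0.989 | 4.7% | 1.8 | 1.6 to 1.7 | 3.3% |
| 1/3/10 | 1.395 | 6.6% | 2.5 | 2.1 to 2.2 | 3.9% |

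Power gains are in percentage points. The simulated column comes from 40,000 paired trials per scenario (7,250 per arm, 4% control risk, HR 1.25, complementary log-log model with and without weight group, shares 87/9/4 or 80/15/5). The Monte Carlo error of the paired difference is about 0.1 point.

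**6. Where the gain comes from.** In those simulations the standard error was about 0.079 with or without weight. The mean log HR was 0.222 unadjusted against 0.224 adjusted (1/2/4), and about 0.219 against 0.223 (1/3/8). The ratio (0.223/0.219)² = 1.037 accounts for most of the simulated z² gain of 4.2 to 4.3% in the latter case. The formula books the gain as if events were added, but it actually arises because the coefficient is less attenuated.

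**7. How often the choice matters.** The significance verdict differed between the two models in 2.4 to 2.8% of trials (1/2/4), 4.7 to 4.8% (1/3/8) and about 5.6% (1/3/10).

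**The case against.** The case against has several parts.

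*Covariates belong in the statistical analysis plan, which is not at hand.* It may well add weight. But 8.2 is not silent: it writes out the primary model down to strata, time scale and clustering. Suggesting a better version of a stated model is fair, provided it is not called an omission or an error.

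*There is nothing to correct.* Randomization makes the comparison valid without weight, and the model respects both randomization strata. This stands in full.

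*No precision is lost.* A reader might infer that leaving weight out widens the confidence interval. The calculations do not support that: the standard error is the same. In a separate run of 1,500 simulated Cox trials with effects 1/2/5, power went from 78.1% to 77.7%. That difference is within Monte Carlo noise for so few runs; the larger simulations show a positive gain in every scenario. Only the word precision has to go.

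*Chance imbalance is small and already inside the confidence interval.* Correct: shifts of 1.7% and 3.3% are ln 1.017/0.079 ≈ 0.2 and ln 1.033/0.079 ≈ 0.4 standard errors. Going to 12,500 per arm shrinks the shift and the standard error alike, so this ratio stays the same. The error rates are sound on average; adjustment helps with the particular allocation drawn.

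*The size rests on assumptions.* It does. Of the 4.0 points of risk, 2.6 are non-fatal infection admissions, and the protocol says nothing about how these vary with weight. Enrolled newborns are clinically stable, and a candidate effect modifier need not be a strong predictor. The upper rows of the table may be out of reach.

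**Conclusion.** The point holds as a minor, optional improvement. Section 8.2 states a primary model without a prognostic covariate, although weight has a place on the inclusion form and a ready categorisation in 8.3. Under the assumed weight effects, adding it gives about 0.2 to 2 points of power and removes a chance shift of roughly 1 to 3% in the hazard ratio (nearly 4% in the most extreme pattern).

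Three further inferences should be resisted. The unadjusted hazard ratio is not biased by imbalance in expectation; any one trial's imbalance is random. Weight cannot be said to be recorded for every newborn, because the form shows fields and the protocol gives no completeness figure. And adjustment is not free: the hazard ratio becomes conditional on weight (log HR about 0.224 against 0.219 to 0.222 unadjusted, at a true HR of 1.25), though that shift is small against a standard error of 0.079, and the planned model is already conditional on sex, place and age.

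**What to change.** Before unblinding, add one sentence to 8.2 and carry it into the statistical analysis plan: the primary Cox model includes inclusion weight as a covariate, in the three categories of 8.3 or as a continuous term (choose one), with the baseline hazards by sex and place of enrollment and the twin clustering kept as they are. State a simple rule for missing weight, such as a separate missing category. Report the same model without weight as a sensitivity analysis. The effect-modification analysis in 8.3 stays unchanged.

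The cost is that sentence, the missing-weight rule, one further modelling choice for weight, and the conditional reading of the hazard ratio. No new data collection and no change in sample size are needed.

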For AD, little is known about the prevalence in Sub-Saharan Africa, but the available data indicate prevalence rates similar to European Union countries, e.g., approx. 12% among 5-year old children.[53] If the cumulative incidence by 2 years of age is 10%, there would be 725 cases of AD in the control group if we recruit 7,250 children in each arm of the trial. We aim to conduct home visits to identify cases of AD until 200 cases have been diagnosed among controls, which would provide power to detect a 28% increase (to 256 intervention group cases) in the risk of AD for children who receive HBV0 and a 25% decrease (to 150 intervention group cases).

For cognitive outcomes, a sample size of 500 will make this study a large study with power to detect clinically meaningful differences in cognitive abilities between children who did or did not receive HBV0.[49]

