4.5 Expected Trial Duration

We expect to be able to enroll 14,500 newborns within 1.5 to 2 years (**Table 3**).

Table 3. Trial timeline with 14,500 enrollments

Period	2026	2027	2028	2029	2030	2031
Events	Enrolment of 14,500 children					
Assessment for morbidity and mortality to 6 weeks	Ongoing	Ongoing	Assessment completed			
Assessment for neurodevelopmental outcomes by 5 years of age					Ongoing	Assessment completed
Assessment for AD by 2 years of age	Ongoing	Ongoing	Ongoing	Ongoing	Assessment completed	

Follow-up will be until 2 years of age for mortality/morbidity. Follow-up for the primary outcome will be finished ~2 years after trial initiation (~1½ years of enrolment with primary follow-up assessed at 6 weeks), while secondary follow-up for morbidity, mortality and AD will continue to 2 years of age. The first 500 children recruited from the HDSS will be followed to 5 years of age for neurodevelopmental outcomes. For this reason, the trial data collection should be finished within <7 years.

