6.3 Randomization Procedures

After informed consent has been obtained, enrolment data will be documented on a written Case Report Form (see below). From a collection of sealed randomization envelopes, prepared in blocks of 24 and stratified by sex and place of inclusion, the mother selects a sealed envelope allocating the neonate 1:1 to the intervention group (HBV0), or the control group (no 3rd vaccine). To avoid confusion at subsequent follow-up, twins of the same sex are only randomized once and allocated the same treatment (the mother only draws one sealed randomization envelope), whereas twins of different sex each will be randomized according to their sex.

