The cumulative incidence of atopic dermatitis will be separately investigated for self-reported cases and physician-diagnosed cases using binomial regression providing RRs, also using the Stata cluster command.

All analyses will be done overall and by sex using Stata software (StataCorp, College Station, Texas), with all estimates reported with 95% confidence intervals.

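### Section 8.2 carries the randomisation strata into the Cox models only, and the cognitive model as stated uses none of the prognostic baseline data collected; the cost is precision, mainly for cognition.

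*Protocol*

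**What the plan says.** Section 6.3 describes envelopes "prepared in blocks of 24 and stratified by sex and place of inclusion". Section 8.2 draws a consequence from this for one family of models: "we will therefore include different underlying baseline hazard functions by sex and place of enrollment in the Cox models".

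The two secondary objectives in section 3.2 use other models. For neurodevelopment: "Cognitive scores will be standardized and tested using linear regression models". For AD: "The cumulative incidence of atopic dermatitis will be separately investigated for self-reported cases and physician-diagnosed cases using binomial regression providing RRs", with clustering added for twin pairs. Neither sentence names a stratum or covariate, and neither says that the model is unadjusted. Section 8.2 closes with: "All analyses will be done overall and by sex using Stata software".

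On the size of the cognitive comparison, section 4.4 says that "a sample size of 500 will make this study a large study with power to detect clinically meaningful differences in cognitive abilities", without an effect size, standard deviation or power. Section 4.5 says who they are: "The first 500 children recruited from the HDSS will be followed to 5 years of age for neurodevelopmental outcomes".

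The inclusion form (section 13.1) records schooling, birth weight and head circumference, all placed before the randomisation entries. Section 8.2 also announces a later document: "The Statistical Analysis Plan (SAP) will be drafted by the trial group and submitted to the DSMB for approval".

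**The concern.** The reason given for stratifying the Cox models is the randomisation itself, so it applies equally to every comparison of the randomised groups. Section 8.2 is specific elsewhere: it fixes strata and clustering for Cox, clustering for case-fatality and AD, and an exact test for sparse counts. An analyst who follows it to the letter would adjust for the strata in the Cox models and leave them out of the cognitive and AD models.

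When strata or baseline variables predict the outcome, leaving them out of a linear model leaves explainable variance in the residual and widens the interval. This matters most where the sample is small and fixed. The cognitive comparison has at most 500 children, and the renewed consent required at 5 years (section 4.2) may reduce that number. Covariates recorded before randomisation are the cheapest remaining source of precision, and fixing the list in advance also rules out a data-driven choice later.

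**Working it through.** **Inputs.** From the protocol: 500 children for cognition (4.4, 4.5), allocated 1:1, so about 250 per arm; AD risk of 10% and 200 control cases, hence 200/0.10 = 2,000 per arm, with 256 or 150 intervention cases (4.4); 80% power and alpha 0.05 (stated in 4.4 for the primary outcome, taken as two-sided and applied here). Assumed: the share of cognitive score variance explained (R²) and the size of the stratum effects. The protocol gives neither.

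**1. The protocol's AD figures.** Power = Φ[(|p1 − p2| − 1.96·SE0)/SE1], with SE0 from the pooled risk and SE1 from the separate risks.
- 10% against 12.8%: SE0 = √(2 × 0.114 × 0.886/2000) = 0.01005, SE1 = 0.01004; (0.028 − 0.01970)/0.01004 = 0.827, power 79.6%.
- 10% against 7.5%: SE0 = 0.00894, SE1 = 0.00893; (0.025 − 0.01751)/0.00893 = 0.839, power 79.9%.

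Both stated effects reproduce at 80% power.

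**2. What the strata would add for AD.** As an approximation, removing between-stratum variance multiplies the SE by √(1 − s), where s is the share of outcome variance between strata. Total variance is 0.10 × 0.90 = 0.09.
- Sex risk ratio 1.5, equal halves: risks 8% and 12%, between-stratum variance 0.02² = 0.0004, s = 0.0044, SE ratio 0.998. Power for the increase goes from 79.6% to 79.8%.
- Sex and place risk ratios both 2.0, four equal cells: s = 0.0261, SE ratio 0.987. Power goes from 79.6% to 80.6% (increase) and from 79.9% to 80.9% (decrease).

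**3. Cognition, strata alone.** The unadjusted SE is √(2/250) = 0.0894 SD. A sex difference of d SD adds variance d²/4. A place difference of d adds d²q(1 − q), where q is the share born outside the main hospital; from section 4.1, q is at most (200 + 700 + 1,000)/9,900 = 0.19.
- Both 0.2 SD: 0.0100 + 0.0062 = 0.0162; R² = 0.0162/1.0162 = 0.016; SE 0.0887.
- Sex 0.3 and place 0.5 SD: 0.0225 + 0.0385 = 0.0610; R² = 0.0575; SE 0.0868.

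A simulation of 500 children randomised in stratified blocks of 24 (3,000 runs per scenario) agrees. Its model SE falls from 0.0895 to 0.0888 and 0.0869, and power rises by 0.4 and 1.8 points. Type I error of the unadjusted model stayed between about 4.0% and 5.2%.

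Place may vary even less. At 15% HDSS residence (4.2), the first 500 HDSS children arise within about 500/0.15 = 3,333 enrolments, in a trial that opens at the main hospital alone.

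**4. Cognition, with baseline covariates.** Detectable difference = (1.960 + 0.842) × √(2(1 − R²)/250) = 0.2506 × √(1 − R²). Equivalent unadjusted sample = 500/(1 − R²).

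| Assumed R² | Detectable difference (SD) | Power at 0.25 SD | Equivalent children |
|---|---|---|---|
| 0 | 0.251 | 79.8% | 500 |
| 0.02 | 0.248 | 80.6% | 510 |
| 0.10 | 0.238 | 83.8% | 556 |
| 0.20 | 0.224 | 87.8% | 625 |
| 0.30 | 0.210 | 91.6% | 714 |

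If only 450 or 400 children are assessed, the unadjusted detectable difference is 0.264 or 0.280 SD. An R² of 0.10 or 0.20 respectively would bring it back to 0.251 SD.

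**The case against.** The strongest reply is that silence is not a decision. Section 8.2 defers detail to a SAP that needs DSMB approval and is to be posted before analysis, and covariates for a secondary outcome are commonly settled there. That stands as far as it goes: a reader might infer that the protocol commits to unadjusted analyses, and it does not say so. What remains is that 8.2 gives a general reason and applies it to one model family only, and a SAP written from it could repeat the asymmetry.

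Three other inferences are tempting and not supported:
- **That AD loses meaningful precision.** The change is about 1 point of power or less, even with stratum risk ratios of 2.0. The case for AD is consistency with the design.
- **That the intervals are invalid.** Omitting strata after stratified randomisation causes no bias; it makes the model SE slightly conservative if anything.
- **That the case-fatality model should be changed too.** That model covers only hospitalised infants, a group formed after randomisation. It may have few events, for which 8.2 already plans Fisher's exact test, and adding strata could produce sparse cells.

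It is also fair to say that sex is not overlooked, since every analysis is repeated by sex. Separate estimates for boys and girls do not adjust the overall estimate, however, and they do nothing for place. Finally, an unadjusted comparison is a valid analysis, and the covariate gain depends on an R² that nobody has yet measured here. Both points stand, and they limit this to an efficiency point.

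**Conclusion.** The point holds as one of efficiency and consistency. Section 8.2 does not carry its own reason for stratifying into the cognitive and AD models, and its cognitive model as stated uses none of the prognostic baseline data collected. No bias follows and no conclusion is put at risk.

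For AD the effect is negligible. For cognition nearly all of the possible gain comes from baseline covariates and very little from the strata: 4 to 12 points of power at 0.25 SD for an R² of 0.10 to 0.30. This rests on the assumed R², on 250 assessed per arm, and on applying the 80% power and two-sided 0.05 convention to an outcome for which the protocol states none.

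**What to change.** Add two sentences to section 8.2 and carry them into the SAP:

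1. The overall AD and cognitive models include sex and place of enrolment, as the Cox models do. For cognition, place is included only if it varies in the assessed subgroup.
2. The cognitive linear model also includes maternal schooling, birth weight and head circumference at inclusion, plus age at test if scores are not age-normed. The list is fixed before unblinding.

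Leave the case-fatality model as it is.

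The cost is small. No new data are needed, and four places plus sex use at most four degrees of freedom. Two practical matters need a line each: a rule for the few missing covariate values, and a named fallback if the AD binomial model fails to converge, such as Poisson regression with robust standard errors that keeps the clustering for twins. An unadjusted estimate can be reported alongside.
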